##### 8.6.4.2 Changes in Cardiometabolic Disease Markers

Descriptive summary tables will be presented for blood pressure (systolic and diastolic blood pressure), fasting lipid profile (total cholesterol, low density lipoprotein [LDL], triglycerides and HDL), HbA1c, fasting glucose, fasting insulin, high sensitivity C reactive protein (hs CRP) and HOMA-IR values and change from baseline values by treatment regimen and visit.

The change from baseline in each parameter up to Week 48 will be analysed via t-test and MMRM in the same manner as the change from baseline in total testosterone (see Section 8.6.3.3). Analyses will be conducted separately for subjects that were randomised to active treatment and subjects that were randomised to placebo treatment in study MBGS205.

Non-fasting values of all lipid profile parameters, glucose and insulin will be excluded from both the descriptive summary and analysis.

In addition the number and proportion of subjects who met the definition of metabolic syndrome will be summarised by treatment regimen at each visit (baseline and post-baseline).

### 8.6.4.3 Change in physical activity, sleeping pattern and strength

#### Physical Activity

Descriptive summary tables will be presented for the average number of minutes spent per day over within each activity category, total daily steps, total daily activity counts and maximum daily activity counts by treatment regimen and visit. The change from baseline in the average number of minutes spent in moderate to very vigorous activity, total daily steps and total activity counts to Week 48 will be analysed in the same manner as the change from baseline in bioavailable testosterone (see Section 8.6.3.5). Analyses will be conducted separately for subjects that were randomised to active treatment (MMRM analysis) and subjects that were randomised to placebo (ANCOVA analysis) in study MBGS205.

#### Sleeping Pattern

Descriptive summary tables will be presented for each sleeping pattern parameter (The average length of awakenings [minutes], number of awakenings, number of minutes asleep [minutes], number of minutes awake [minutes] and proportion of time spent asleep during the sleep period) and associated change from baseline by treatment regimen and visit. The change from baseline in each parameter to Week 48 will be analysed in the same manner as the change from baseline in bioavailable testosterone (see Section 8.6.3.5). Analyses will be conducted separately for subjects that were randomised to active treatment (MMRM analysis) and subjects that were randomised to placebo (ANCOVA analysis) in study MBGS205.

#### Grip Strength

A descriptive summary table will be presented for the average grip strength and associated change from baseline by treatment regimen and visit. The change from baseline in average grip strength to Week 48 will be analysed via MMRM in the same manner as the change from baseline in total testosterone (see Section 8.6.3.3). Analyses will be conducted separately for subjects that were randomised to active treatment and subjects that were randomised to placebo treatment in study MBGS205.

A subgroup analysis of the change from baseline in grip strength by baseline total testosterone (<200ng/dL vs ≥200ng/dL) as assessed by ICON central labs will be conducted. Descriptive summaries and analysis up to Week 48 as described above will be presented.

### 8.6.4.4 Change in PRO measures

For some PRO Measures (PROMIS SexFS, PROMIS Fatigue Short Form and PGI-S), not all MBGS205 protocol versions mandated their collection. Thus for subjects originally enrolled into

study MBGS205 using protocol version 2.0 MBGS206, baseline will be the first time these measures were collected. To handle such cases, these subjects will be excluded from the change from MBGS205 baseline to Week 48 analysis (if randomised to active treatment in Study MBGS205), however will still be included in the descriptive summary tables.

### IIEF

Descriptive summary tables will be presented for each of the 5 sexual function domain scores (Erectile function, Orgasmic function, Sexual desire, Intercourse satisfaction and Overall satisfaction) and change from baseline scores by treatment regimen and visit.

The change from baseline in each sexual function domain score to Week 48 will be analysed via MMRM in the same manner as the change from baseline in total testosterone (see Section 8.6.3.3), however 90% confidence intervals (instead of 95%) will be presented for all inferences. Analyses will be conducted separately for subjects that were randomised to active treatment and subjects that were randomised to placebo treatment in study MBGS205. A figure presenting the least square mean change from baseline in each sexual function domain at each visit by treatment regimen will also be provided.

The number and proportion of subjects achieving a minimal meaningful difference in the change in IIEF erectile function domain score will be summarised by treatment regimen at each visit and overall.

In addition the change from baseline in the IIEF domains will also be summarised and analysed as described above by erectile function baseline severity (No dysfunction, mild, moderate and severe), baseline total testosterone (<200ng/dL vs ≥200ng/dL) as assessed by ICON central labs and end of treatment total testosterone (<300ng/dL, 300-500 ng/dL and >500ng/dL) as assessed by ICON central labs.

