The doses of BGS649 [REDACTED] and dosing schedule [REDACTED] selected for use in Study MBGS205 were chosen based on results obtained in a previous study in obese male subjects with HH, which suggested that these doses were well tolerated and may normalise testosterone levels (Study CBGS649A2204). To assure 12 months each dose arm study drug exposure, subjects will continue with the same active study drug assignment from Study MBGS205 to the Study MBGS206. To keep the study blinded and offer subjects receiving placebo the benefit of active arm treatment, the placebo subjects in Study MBGS205 will be randomised to one of the active treatment arms. If one or more dosing arms are dropped during the conduct of Study MBGS205, these will not be progressed in Study MBGS206.

Aromatase inhibitors decrease oestrogen synthesis and increase pituitary luteinising hormone (LH) and follicle stimulating hormone (FSH) with a consequent stimulation of testosterone

production (de Boer et al 2005; Loves et al 2008). This increase in testosterone has multiple clinical effects, including: effect on insulin resistance, on body composition, strength and sexual and overall well-being. Therefore, additional safety, efficacy, and pharmacokinetic (PK) will be collected in subjects who completed the full 24 week treatment period in Study MBGS205. It is conceivable that up to 12 month exposure may be needed to demonstrate full treatment benefit in regards to positive effect on cardiometabolic parameters (Haider et al 2010). In addition, the improvement in body composition may be also shown consistently only after 12 months treatment (Emmelot-Vonk et al 2008).

Testosterone increase may lead to worsening certain parameters e.g. prostate-specific antigen (PSA), haematocrit. To ensure adequate safety monitoring, these parameters together with testosterone level will be monitored in the same way as in MBGS205 study (see Section 9.1.1 for a detailed description)

BGS649 has been shown to be present in semen. PK assessment of seminal fluid and plasma will be performed to determine the plasma/semen relationship to enable modelling of BGS649 semen concentration by dose in order to determine the potential transference of BGS649 to sexual partners.

This study will be conducted in compliance with the protocol and with the International Conference on Harmonisation (ICH) guidelines on Good Clinical Practice (GCP).

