### 8.1.4 Statistical significance

Unless otherwise stated, all statistical testing will be two-sided and conducted at the significance (alpha) level of 0.05. Two-sided 95% confidence intervals (CIs) will be provided when relevant. Treatment regimens will be assessed by pairwise comparisons, and no adjustment for multiplicity will be made.

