##### 8.6.1.1 Multiplicity

Treatment regimens will be assessed by pairwise comparisons. No adjustment will be made for multiple comparisons and all analyses are considered exploratory.

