#### 8.6.3.3 Change from Baseline in Total Testosterone

A descriptive summary table will be presented for Total Testosterone values and percentage change from baseline in Total Testosterone values by treatment regimen and visit using both ICON central lab assessed testosterone.

A single sample 2-sided t-test conducted at the 5% significance level will be used to analyse the percentage change from Baseline at Week 48 within each treatment arm. The p-value and associated confidence interval will be presented.

In addition the percentage change from baseline in Total Testosterone up to Week 48 for subjects randomised to active in Study MBGS206 using the ICON central lab assessed values will be analysed using an MMRM model as described in Section 8.6.1. Least squares means and standard

errors will be presented for each visit, p-value and 2-sided 95% confidence interval for treatment differences will be presented for each visit. Significance tests will be based on least-squares means using a two-sided  $\alpha = .05$ .

A figure presenting the least square mean change from baseline in total testosterone at each visit by treatment regimen will also be provided.

The above analyses will be repeated for subjects that were randomised to placebo in Study MBGS205 by analysing the change from MBGS206 baseline (Week 24) to Week 48.

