### SF-36

Descriptive summary tables will be presented for each of the 8 general health domain scores and 2 component scores and change from baseline scores by treatment regimen and visit.

The change from baseline in each domain and component score to Week 48 will be analysed via MMRM in the same manner as the change from baseline in IIEF domain scores including subgroup analysis by baseline total testosterone (<200ng/dL vs ≥200ng/dL) and end of treatment total testosterone (<300ng/dL, 300-500 ng/dL and >500ng/dL) as assessed by ICON central labs.

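### Patient-reported outcome dose contrasts within end-of-treatment testosterone strata do not estimate the randomised dose effect if the doses differ in their effect on testosterone

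*SAP*

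**What the plan says.** In the IIEF part of SAP 8.6.4.4, the change in each domain "will also be summarised and analysed as described above by erectile function baseline severity", by baseline total testosterone, and by "end of treatment total testosterone (<300ng/dL, 300-500 ng/dL and >500ng/dL) as assessed by ICON central labs". The analysis it points back to is the mixed model of SAP 8.6.3.3, where "p-value and 2-sided 95% confidence interval for treatment differences will be presented for each visit". The IIEF text alters only the confidence level: "however 90% confidence intervals (instead of 95%) will be presented for all inferences". So dose inference is planned within the strata, not only description.

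The other PROs inherit this. For SF-36, for example, the change is "analysed via MMRM in the same manner as the change from baseline in IIEF domain scores including subgroup analysis by baseline total testosterone", and the same sentence goes on to name the three end-of-treatment strata. PROMIS SexFS, PROMIS Fatigue, BFI and PGI-S have matching sentences. The analyses are run separately for men active in MBGS205 and men switched from placebo.

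On multiplicity, SAP 8.1.4 states: "Treatment regimens will be assessed by pairwise comparisons, and no adjustment for multiplicity will be made". SAP 8.6.1.1 adds: "No adjustment will be made for multiple comparisons and all analyses are considered exploratory". The SAP attaches no caveat, estimand or causal method to the end-of-treatment strata.

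**The concern.** End-of-treatment testosterone is an outcome of treatment. Protocol 7.2 says that aromatase inhibitors "increase pituitary luteinising hormone (LH) and follicle stimulating hormone (FSH) with a consequent stimulation of testosterone" production, and that this rise has effects on sexual and overall well-being. SAP 8.6.3.1 compares testosterone normalisation between doses, so the SAP treats testosterone as something that dose may change.

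If one dose raises testosterone more than another, men who finish in the same stratum on the two doses are different kinds of men. A man at 400 ng/dL on the stronger dose has responded poorly relative to his group; a man at 400 on the weaker dose may be typical of his. Two things follow:

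- **Shared causes.** Where testosterone and the PRO have common determinants, the contrast picks up that selection and can show a difference that dose did not cause.
- **Mediation.** Where testosterone carries the benefit, holding it roughly fixed removes part of a real dose effect.

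At stake is interpretation. In a dose-ranging programme, a p-value suggesting that a higher dose does worse at a given achieved testosterone level could be read as a finding about dose. The mixed model also reports earlier visits such as Week 36, which would be stratified by a testosterone value measured later.

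**Working it through.** **Inputs from the documents.** Strata cut at 300 and 500 ng/dL; three doses compared pairwise; about 25 completers per dose (protocol synopsis: 30 entered, 17% dropout; 30 × 0.83 = 24.9, so the plan's figure reproduces).

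**Assumed inputs.** Testosterone is normal with SD 150 ng/dL in each dose group; PRO-change SD is 6 points; the testosterone-PRO correlation r is 0.2 or 0.4, read as what remains after the model's baseline adjustment. The documents give no testosterone mean or SD by dose, so the dose means are varied, starting from equality.

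**Case A: shared causes only, no dose effect on the PRO.** For a dose with mean m and a stratum from L to U, let a = (L − m)/150 and b = (U − m)/150. The mean standardised testosterone in the stratum is z = [φ(a) − φ(b)] / [Φ(b) − Φ(a)]. The artefact, higher minus lower dose, is 6 × r × (z_high − z_low). In the 300-500 stratum:

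| Dose means (ng/dL) | z low | z high | Difference | r = 0.2 | r = 0.4 |
|---|---|---|---|---|---|
| 450 vs 450 | -0.287 | -0.287 | 0 | 0 | 0 |
| 440 vs 490 | -0.230 | -0.517 | -0.288 | -0.35 | -0.69 |
| 400 vs 560 | 0 | -0.922 | -0.922 | -1.11 | -2.21 |

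(Differences are taken before rounding.) In the >500 stratum, 400 vs 560 gives z of 1.265 and 0.562, hence -0.84 and -1.69 points. The true effect is zero throughout.

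**Case B: testosterone carries the whole effect, no shared cause.** The slope is r × 6/150, which is 0.008 or 0.016 points per ng/dL. At 400 vs 560 the true total effect is 160 × 0.008 = 1.28, or 160 × 0.016 = 2.56 points. Within strata, only the remaining gap in mean testosterone counts:

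| Stratum | Mean testosterone, low vs high dose | Gap | r = 0.2 | r = 0.4 |
|---|---|---|---|---|
| <300 | 210.2 vs 239.1 | 28.9 | +0.23 | +0.46 |
| 300-500 | 400.0 vs 421.7 | 21.7 | +0.17 | +0.35 |
| >500 | 589.8 vs 644.3 | 54.5 | +0.44 | +0.87 |

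A real +1.3 to +2.6 therefore appears as about +0.2 to +0.9.

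**Both mechanisms together.** A simulation of 1,000,000 men per dose used dose means of 400, 475 and 550, a slope of 0.4 PRO SD per testosterone SD, and a shared cause explaining 40% of testosterone variance and 30% of the PRO's residual variance. The unstratified difference between the highest and lowest dose was +0.40 SD. Within strata it was -0.10 to -0.24 SD, so the sign can reverse.

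**Cell sizes for 25 men per dose** (25 × probability of falling in the stratum, in the order <300, 300-500, >500): mean 400 gives 6.3, 12.4, 6.3; mean 560 gives 1.0, 7.6, 16.4; mean 450 gives 4.0, 11.8, 9.2.

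**Number of contrasts.** IIEF 5 + SexFS 3 + Fatigue 1 + BFI 1 + SF-36 10 + PGI-S 3 = 23 scores. 23 × 3 strata × 3 dose pairs = 207 unadjusted Week 48 contrasts per cohort, or 414 over both.

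**The case against.** The strongest reply is that the bias is conditional. The protocol shows that the drug raises testosterone; it does not show that the three active doses raise it by different amounts, and MBGS206 has no placebo arm. SAP 3.1 records that all three doses met the efficacy and safety criteria at the MBGS205 interim analysis. That does not prove equal effects, but it gives no support for a large gap. With equal dose means the artefact is exactly zero. This stands, and it is why the range starts at zero.

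A reader might infer that a dose with no PRO benefit will show a spurious difference, or that the higher dose will look worse. The documents support neither. The negative direction belongs to the shared-cause model. The path the protocol describes runs from testosterone to well-being, and on its own that path gives attenuation, not apparent harm.

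The analyses are also exploratory and no decision rule uses them. That limits the consequence, but the label deals with multiplicity, not with whether a contrast means what it appears to mean.

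Finally, small cells are not peculiar to these strata: the four baseline erectile-function categories divide the same 25 men. Sparse cells are a secondary point here, not the ground for the change.

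**Conclusion.** The concern holds in conditional form and is minor. The SAP plans between-dose p-values and 90% intervals within strata of a post-dosing outcome on the drug's pathway. If the doses differ in their effect on testosterone, and testosterone and the PRO share causes or testosterone mediates the PRO effect, those contrasts do not estimate the randomised dose effect.

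Under the stated assumptions the artefact ranges from nothing to about 2 points. For scale, SAP 7.1.3.3 sets the minimal meaningful change in the IIEF erectile function domain at 2 points for men who are mild at baseline and 5 or 7 for worse categories. The SD of 6 is not tied to any one instrument, so this comparison is only indicative. Neither the size nor the sign can be fixed from the documents.

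The baseline-severity and baseline-testosterone subgroups do not share the problem, because under SAP 8.1.5 baseline is taken on or before the first active dose.

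**What to change.** In SAP 8.6.4.4:

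1. Keep the baseline-severity and baseline-testosterone subgroup models as planned.
2. For the end-of-treatment testosterone strata, in all six PRO subsections, present descriptive summaries only, pooled over dose within each cohort. Give no between-dose p-values or confidence intervals, and add a note that the tables are non-causal.
3. Address the testosterone-PRO relation through the regressions already planned in SAP 8.8.3, with the same non-causal label, since they too are open to confounding.

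The work is a text change and fewer tables. The cost is that there is no dose inference by achieved testosterone level. Also, SAP 8.8.3 covers only men who were active in MBGS205, so the placebo-switch cohort keeps only descriptive tables for this question unless 8.8.3 is extended to it.

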### PROMIS SexFS

Descriptive summary tables will be presented for each of the 3 sexual function domains scores (Interest in Sexual Activity, Erectile Function, Satisfaction with Sex Life) 2 interfering factors raw scores and change from baseline scores (domain and interfering factor raw scores) by treatment regimen and visit.

The change from baseline in each sexual function domain score to Week 48 will be analysed via MMRM in the same manner as the change from baseline in IIEF domain scores including subgroup analysis by baseline total testosterone (<200ng/dL vs ≥200ng/dL) and end of treatment total testosterone (<300ng/dL, 300-500 ng/dL and >500ng/dL) as assessed by ICON central labs.

### PROMIS Fatigue Short Form

A descriptive summary table will be presented for the PROMIS Fatigue Short Form standardised T-Score and change from baseline score by treatment regimen and visit.

The change from baseline to Week 48 will be analysed via MMRM in the same manner as the change from baseline in IIEF domain scores including subgroup analysis by baseline total testosterone (<200ng/dL vs ≥200ng/dL) and end of treatment total testosterone (<300ng/dL, 300-500 ng/dL and >500ng/dL) as assessed by ICON central labs.

### BFI

A descriptive summary table will be presented for the global fatigue score and change from baseline score by treatment regimen and visit.

The change from baseline to Week 48 will be analysed via MMRM in the same manner as the change from baseline in IIEF domain scores including subgroup analysis by baseline total testosterone (<200ng/dL vs ≥200ng/dL) and end of treatment total testosterone (<300ng/dL, 300-500 ng/dL and >500ng/dL) as assessed by ICON central labs.

### SF-36

Descriptive summary tables will be presented for each of the 8 general health domain scores and 2 component scores and change from baseline scores by treatment regimen and visit.

The change from baseline in each domain and component score to Week 48 will be analysed via MMRM in the same manner as the change from baseline in IIEF domain scores including subgroup analysis by baseline total testosterone (<200ng/dL vs ≥200ng/dL) and end of treatment total testosterone (<300ng/dL, 300-500 ng/dL and >500ng/dL) as assessed by ICON central labs.

### PGI-S

Descriptive summary tables will be presented for each of the 3 status items and associated change from baseline scores by treatment regimen and visit.

The change from baseline in each status item to Week 48 will be analysed via MMRM in the same manner as the change from baseline in IIEF domain scores including subgroup analysis by baseline total testosterone (<200ng/dL vs ≥200ng/dL) and end of treatment total testosterone (<300ng/dL, 300-500 ng/dL and >500ng/dL) as assessed by ICON central labs.

## **8.7 Safety analyses**

All definitions relative to safety endpoints are detailed in Section 7.1.4.

All safety analyses will be based on the Safety population and will be performed for all safety endpoints specified below.

### **8.7.1 DXA Scans**

DXA Scan assessments will only be performed at the EOT visit (for subjects that reached at least Week 36) and will be over-read by IMI. Both the site assessed and the over-read data will be used for all statistical analysis and utilise the visit windows specified in Appendix F. If multiple assessments are recorded within the window, the closest to the target date will be used for analysis.

Descriptive statistics (observed values, changes from baseline and percentage change from baseline) in hip (total and femoral neck) bone density will be presented. In addition descriptive statistics (observed values and changes from baseline) for the associated T-scores in both the lumbar spine and hip will be presented for each treatment regimen and time-point.

A shift table of baseline severity categories (Normal, Osteopenia and Osteoporosis) to post baseline severities will be generated by treatment regimen and visit.

Change from baseline in bone density (in both the lumbar spine and hip) to Week 48 for subject randomised to active treatment in Study MBGS205 will be analysed via MMRM in the same manner as the change from baseline in total testosterone (see Section 8.6.3.3).

Change from baseline in bone density (in both the lumbar spine and hip) to Week 48 for subjects randomised to placebo in Study MBGS205 will be analysed using an ANCOVA model with treatment as a fixed effect and the associated baseline value as a covariate. Least squares means and standard errors will be presented for each visit, p-value and 2-sided 95% confidence interval for treatment differences across all doses will be presented for each visit. Significance tests will be based on least-squares means using a two-sided  $\alpha = .05$ .

In addition subgroup descriptive summary tables of change in bone density by subjects with and without 25 hydroxy vitamin D deficiency at baseline (vitamin D deficiency is defined as 25 hydroxy vitamin D < 30ng/ml) will be presented.

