12.4 DEXA Scan

Bone density will be evaluated with standard procedure described in study imaging manual. All evaluations during the study for particular subject should, where possible, be performed on the same machine with particular attention to ensuring consistency in positioning patients.

To assess the spine, the subject will be in supine position with legs supported on a padded box to flatten the pelvis and lower (lumbar) spine. To assess the hip, the foot is placed in a brace that rotates the hip inward. The detector will be slowly passed over the area separately for spine and hip, generating images. The duration of examination will be up to 30 minutes. DEXA T Score will be calculated based on actual measured bone density value. Both values will be evaluated for safety.

EOT DEXA scan: If the subject is discontinued from the treatment early, DEXA will be performed only if they reached minimum Week 36 (Visit 4) active treatment period. In order to accommodate scheduling, EOT DEXA can be performed within 5 days before the EOT visit

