13.5.3 Analysis of Secondary Endpoints

13.5.3.1 Safety

The analysis of secondary safety endpoints will be performed using the safety population.

The percentage change from Baseline in hip bone mineral density measured in g/cm² by DEXA will be summarised by treatment arm and visit. A single sample 1-sided t-test conducted at the 2.5% significance level will be used to analysis percentage change from Baseline (MBGS205) at Week 48 (MBGS206) in each treatment arm to test the null hypothesis that the percentage decrease from Baseline is $\leq 3\%$. Only subjects that have a post-Baseline DEXA assessment in MBGS206 will be included in this analysis.

The percentage change from Baseline in bone turnover markers, bone density, bone biomarkers and oestradiol (absolute and percentage) will be summarised by treatment arm and visit. A 95% CI will be presented for the mean change at each visit.

The proportion of subject with a T-score ≤ -2.5 at Week 48 will be summarised by treatment arm and visit. A 95% CI will be presented for the proportion of subjects with a T-score ≤ -2.5 .

The proportion of subjects with testosterone ≤ 1000 ng/dl (35 nmol/L) and > 1000 ng/dl (35 nmol/L) will be summarised by treatment arm and visit.

TEAEs will be summarised per [Section 13.5.5](#). For subjects randomised to active treatment in Study MBGS205 first dose is considered as the first dose in Study MBGS205. For subjects randomised to placebo in Study MBGS205 first dose is considered as the first dose in Study MBGS206.

A more detailed description will be presented in the SAP.

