### 6.1 Intention-To-Treat population (ITT)

The ITT population includes all subjects who:

1. Are randomised, and
2. Receive at least one dose of MBGS206 study medication, and
3. Provide a baseline (see section 8.1.5 for full definition of baseline) primary endpoint safety value (lumbar spine) and at least 1 available evaluation of primary endpoint safety value (lumbar spine) post- Baseline in MBGS206.

Subjects will be analysed according to the treatment to which they were randomised.

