## 7.2 Handling of missing data and outliers

### 7.2.1 Missing data analysis methods

Unless specified, data in summary tables will be presented using Observed Case (OC) data and therefore no missing data will be imputed.

For specified endpoints a last observation carried forward (LOCF) imputation will be utilised. In this approach subjects with a missing observed value at a visit will be imputed with the last non-missing, post-baseline value.

For each continuous exploratory endpoint, the change from Baseline will be assessed with a mixed model repeated measure (MMRM) analysis.

For data listings, unless specified, all data will be presented as they have been recorded (e.g. missing and partial dates will not be replaced).

---

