#### 8.1.1 Populations for analysis

Demographic and baseline characteristics will be summarised by Safety, Completers and ITT populations, unless otherwise stated.

Analyses of the primary endpoint and secondary safety BMD endpoints will be performed on ITT and completer population. Analysis of all other safety endpoints will use the safety population.

The secondary efficacy endpoints and exploratory endpoints will be analysed using the ITT population.

The safety and tolerability variables will be analysed using the Safety population.

PK data will be analysed using the PK population.

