#### 8.1.3 Descriptive statistics

Continuous variables will be summarised using descriptive statistics including number of non-missing observations (n), arithmetic mean (Mean), median (Median), standard deviation (SD), minimum value (Min) , maximum value (Max) and number of missing observations (if any). One additional decimal point for mean and median and 2 additional decimal points for SD will be used.

For categorical variables, summaries will include the number of non-missing observations (n) or the number of patients in the population (N) as applicable, the counts of subjects and percentages. Percentages will be rounded to one decimal place. The number of missing values will be presented as a separate category with no percentage, but only if any missing value is recorded in the data for that summary.

Summary statistics will only be presented at each visit for which the parameter is scheduled to be

collected.

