### 9 CHANGES TO PLANNED ANALYSIS FROM STUDY PROTOCOL

The below are changes to the study protocol analysis:

The Percentage change in lumbar bone mineral density measured by DEXA (g/cm^2) from Baseline in Study MBGS206 to Week 48 for subjects that were randomised to placebo in Study MBGS205 has been added as a secondary safety endpoint. This was inadvertently absent from the study protocol.

Vitamin D deficiency is defined in the protocol as <20ng/ml. For all analyses Vitamin D deficiency has been defined as <30ng/ml.

Following data integrity concerns at site 1156, sensitivity analyses were added to assess the impact of the site on key parameters.

---

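### SAP 8.7.1 and Appendix F leave the end-of-treatment DXA scans of men who stop between Week 36 and about Week 43–44 without a visit row, and 8.6.2 does not say whether the same windows bind the primary analysis

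*SAP*

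**What the plan says.** **When a scan is due.** For men who stop early, Protocol 12.4 states that "DEXA will be performed only if they reached minimum Week 36 (Visit 4) active treatment period". SAP 8.7.1 repeats the Week 36 condition. Protocol 9.3.4 puts the early EOT visit within 7 days of stopping.

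**How scans are placed.** SAP 8.7.1: "Both the site assessed and the over-read data will be used for all statistical analysis and utilise the visit windows specified in Appendix F". For men on active drug in MBGS205, Appendix F gives post-baseline windows of Days 140–196 (Week 24) and Day 308 to end of study (Week 48). For placebo-switch men the only post-baseline window runs from Day 140 to end of study. Study day counts from the first active dose (SAP 7.1.1).

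**Missing values.** SAP 7.2.1: "Unless specified, data in summary tables will be presented using Observed Case (OC) data and therefore no missing data will be imputed". LOCF is kept for endpoints that specify it. Section 8.7.1 specifies none; 8.6.2 (primary) does. SAP 8.1.3 adds: "Summary statistics will only be presented at each visit for which the parameter is scheduled".

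**Who is analysed.** SAP 8.1.1: "Analyses of the primary endpoint and secondary safety BMD endpoints will be performed on ITT and completer population". ITT entry under 6.1 needs "at least 1 available evaluation of primary endpoint safety value (lumbar spine") after baseline in MBGS206, with no window stated. SAP 8.7 puts safety analyses in general on the Safety population.

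**The concern.** One rule asks for a scan, and a later rule gives that scan nowhere to go. The same scan, with no window attached, admits the man to ITT, the population for the secondary BMD endpoints.

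The men concerned may not be a random subset. Protocol 9.3.4 lists fragility fracture and two consecutive total testosterone values of 1500 ng/dL or more among the mandatory reasons to stop. This extension exists to show bone effects, and the extension-period hip result of a man stopped for such a reason could be absent from every 8.7.1 table.

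A second uncertainty concerns the primary analysis. Section 8.6.2 uses LOCF to Week 48 but does not mention Appendix F, while 8.7.1 speaks of all statistical analysis. If the windows apply to 8.6.2, an unplaced EOT scan could be passed over and the MBGS205 Week 24 scan carried forward in its place.

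**Working it through.** **1. The plan's own figure.** The protocol synopsis plans 30 entrants per previous active arm, about 17% dropout and about 25 completers. 30 × (1 − 0.17) = 24.9, which reproduces 25. Dropouts: 0.17 × 30 = 5.1, taken as 5.

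**2. Windows in weeks.** 336/7 = 48 and 308/7 = 44 for active men. For placebo-switch men 168/7 = 24 and 140/7 = 20 weeks after the switch, and 20 weeks is study Week 44. Week 36 (Visit 4) is Day 36 × 7 = 252 for active men and Day (36 − 24) × 7 = 84 for placebo-switch men. The nominal gaps are Days 252–307 and Days 84–139, each 56 days of the 84 between Week 36 and Week 48 (67%).

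**3. Actual scan days.** Allow visit ±2 days, EOT visit 0–7 days after stopping, and scan ±5 days (Protocol Table 9–1, footnote 11).

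| Stop at | Active: scan days | Placebo-switch: scan days | In a window |
|---|---|---|---|
| Week 36 | 245–266 | 77–98 | none |
| Week 40 | 273–294 | 105–126 | none |
| Week 42 | 287–308 | 119–140 | last day only |
| Week 43 | 294–315 | 126–147 | 8 of 22 days |
| Week 44 | 301–322 | 133–154 | 15 of 22 days |
| Week 46 | 315–336 | 147–168 | all |

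**4. Stopping days that lead to an unplaced scan (active).**
- Always, if the scan may follow the visit by 5 days: stop + 7 + 5 ≤ 307, so Days 252–295, 44/84 = 52%.
- Always, if it may only precede the visit: stop + 7 ≤ 307, so Days 252–300, 49/84 = 58%.
- At most: stop − 5 ≤ 307, so Days 252–312, 61/84 = 73%.

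Placebo-switch men have the same counts (Days 84–127, 84–132 and 84–144).

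**5. Men per active arm.** Assumption: 5 dropouts, stopping uniformly over 168 days. After Week 36: 5 × 84/168 = 2.5. Unplaced: 5 × 44/168 = 1.31; 5 × 49/168 = 1.46; nominal 5 × 56/168 = 1.67; at most 5 × 61/168 = 1.82. Without the uniform assumption the range is 0–5. The documents give no number per arm for placebo-switch men.

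**6. What each man loses under 8.7.1.**
- Active: his Week 48 hip BMD, T-score and shift entry, and his Week 48 MMRM value. His baseline and Week 24 values stay in the tables, and the Week 24 value stays in the MMRM.
- Placebo-switch: every post-baseline DXA value, including those for the lumbar and hip ANCOVA.

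**7. Illustrations.** With 25 completers, leaving out one man with a T-score of −2.5 or lower gives 0/25 (exact 95% upper limit 13.7%) instead of 1/26 (3.8%, 0.1–19.6%). If early stoppers lose d percentage points more hip BMD than completers, leaving out k men understates the raw mean loss by k/(25 + k) × d. With k = 1–2 and d = 1–3 (assumed), this runs from 1/26 × 1 = 0.04 to 2/27 × 3 = 0.22 points. The sign reverses if they lose less.

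**The case against.** **Nothing says that the scan is excluded.** The actigraphy text (SAP 7.1.3.9) restricts analysis to data inside its windows; 8.7.1 has no such restriction. An early stopper also has the assessments of the Week 48 visit (Protocol 9.3.4), which is a scheduled DXA visit. This stands in part: the fault is an unstated assignment, not a stated exclusion. But 8.7.1 places scans by day, and no rule moves an early EOT scan into the Week 48 row.

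**Active men do not vanish.** A reader might infer that they are missing from the bone outputs altogether. They are not, as step 6 shows.

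**ITT may not govern every output.** Section 8.1.1 reserves ITT and completers for BMD endpoints, so T-score and shift outputs may follow the Safety population, which men enter by dosing. That is right, but the scan is equally unplaced there.

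**The primary test.** A reader might infer that it is certainly safe. Section 8.6.2 requires an MBGS206 scan, and only one is scheduled after baseline, so LOCF there does most if it carries the man's own early scan. Section 8.6.2 also names only the over-read data, whereas 8.7.1 names both readings, which suggests that the 8.7.1 sentence was not written for it. These points favour that reading but do not settle it.

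**The protocol.** A reader might infer a breach of Protocol 13.5.3.1, which says of the hip test "Only subjects that have a post-Baseline DEXA assessment in MBGS206 will be included in this analysis", because SAP Section 9, under "The below are changes to the study protocol analysis", does not mention the windows. The documents do not support that. The same paragraph analyses change at Week 48, the sentence is an entry condition for a one-sample test that 8.7.1 does not contain, and Protocol 13.5.1 presents tables generally as observed cases.

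**Other safeguards and the illustrations.** Fragility fracture and a T-score of −2.5 or lower are both AESIs (Protocol 12.1.7), so they reach the AE tables, and scans are listed. All analyses are exploratory. The T-score example needs a fall of at least 0.5 within the extension, because men below −2.0 are not enrolled, and 8.7.1 describes no table of that proportion, although Protocol 13.5.3.1 does. The 73% bound needs a scan before an unplanned stop. All of this stands and keeps the point small. None of it shows the hip BMD change of an early stopper.

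**Conclusion.** The point holds in limited form. EOT scans required from men who stop between Week 36 and about Week 43–44 have no Appendix F window, and nothing in 8.7.1 rescues them. Active men lose their only extension-period entry; placebo-switch men lose all post-baseline DXA data. Whether the primary analysis is touched cannot be decided from the text, because 8.6.2 is silent on Appendix F.

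The size rests on the 17% dropout figure and on uniform stopping, which is my assumption; stops clustered before Week 36 or after Week 44 would bring it towards zero. The effect on the hip mean rests on an assumed difference and could go either way. Keeping a Week 36 scan out of a Week 48 row is defensible in itself. The reason to act is that on-treatment bone data from men who may have stopped for safety reasons should appear somewhere in the tables, and that the SAP should say which scan LOCF uses.

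**What to change.** 1. **Appendix F:** add an Early EOT record, defined as an MBGS206 EOT DXA before Day 308 (active in MBGS205) or before Day 140 (placebo-switch).
2. **SAP 8.7.1:** show hip BMD, T-scores and the severity shift at Week 48 (observed, unchanged) and, beside it, at the last MBGS206 scan (Week 48 or Early EOT). Repeat the placebo-switch ANCOVA on the last MBGS206 scan. Leave the MMRM unchanged. State the population for the T-score and shift outputs.
3. **SAP 8.6.2:** state that LOCF uses the last MBGS206 scan and that no MBGS205 scan is carried forward.
4. **Scan allowance:** Protocol Table 9–1 footnote 11 allows 5 days before or after the EOT visit; Protocol 12.4 and SAP Table 1 footnote 11 mention only 5 days before. These must be reconciled.

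If the sponsor means to leave these scans out of the tables, 8.7.1 should say so.

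**Cost:** one record label, one extra row in three sets of tables, and one repeated ANCOVA; no new data. **Downside:** the added row mixes about 36–48 weeks of exposure (12–24 weeks in placebo-switch men), so it supplements the Week 48 row and does not replace it.
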